**Sample Size Considerations:**

There is no published data on which to base power calculations for this study.

Prior studies have demonstrated that chlorhexidine mouthwash significantly reduces *F. nucleatum* in the mouth. However, these studies used older techniques to quantify *F. nucleatum*, and the results cannot be readily translated to expected findings using qPCR.

A sample size of 20 subjects (10 per arm) has 83% power (assuming  $\alpha = 0.05$ ) to detect a 1.3 SD difference in mean *F. nucleatum* between the groups, which likely represents a biologically meaningful difference. As this is a pilot study, we believe that in the event no significant reduction in *F. nucleatum* is observed, we will still obtain valuable data from the secondary analyses that will assist in the design of future studies aimed at altering the microbiome to reduce the risk of BE and EAC.

We anticipate that 10% of enrolled subjects will be excluded, removed, or lost to follow-up. We therefore plan to enroll 22 subjects.

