The esophageal microbiome is very similar to the oral microbiome; both contain an abundance of anaerobes as well as a high ratio of Firmicutes to Bacteroidetes. The microbiome of the upper gastrointestinal tract is presumably heavily influenced by migration of bacteria from the mouth via swallowed secretions. Therefore, it stands to reason that altering the oral microbiome can directly impact the microbiome of the esophagus and gastric cardia. Chlorhexidine has broad antimicrobial effects, and chlorhexidine-based mouthwashes have been used clinically for many years in the treatment of gingival and other oral diseases. Chlorhexidine mouthwash effectively reduces anaerobes and *F. nucleatum* in particular in the mouth. It also has anti-inflammatory effects (likely due to reductions in pro-inflammatory bacteria), and protects against mucositis in chemotherapy patients. We therefore propose to perform a randomized open-label pilot study to assess the effects of chlorhexidine mouthwash on the microbiome of the gastric cardia. The results of this study provide valuable information as to whether altering the oral microbiome can serve as a novel chemopreventive intervention to reduce the risk of esophageal adenocarcinoma.

This is a randomized, open-label pilot study to assess whether treatment with chlorhexidine mouthwash can alter the esophageal and gastric cardia microbiome.

We will enroll a total of 20 subjects. Patients scheduled for upper endoscopy for clinical indications will be randomized to 2 weeks of either no treatment or use of twice daily chlorhexidine mouthwash leading up to the endoscopy.

The hypotheses to be tested are:

1. Treatment with chlorhexidine mouthwash will significantly reduce the absolute abundance of *F. nucleatum* in saliva.
2. Subjects treated with chlorhexidine mouthwash will have significantly lower absolute abundance of *F. nucleatum* in the gastric cardia, compared to subjects who receive no treatment.

We will enroll patients scheduled for upper endoscopy by their treating physician and who meet the inclusion and exclusion criteria. There will be 2-3 study visits, at Day 0 and Day 14, and for

those subjects in the mouthwash arm, a final visit 1-2 weeks following the Day 14 visit. Subjects will be required to fast overnight prior to the visits on Days 0 and 14.

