**Statistics:**

The primary outcome will be the absolute abundance of *F. nucleatum*. To address the hypothesis that chlorhexidine mouthwash reduces the absolute abundance of *F. nucleatum* in the mouth, we will assess within individual differences in subjects treated with chlorhexidine and in those who received no treatment.

We will calculate mean and standard deviation for the within-individual change in *F. nucleatum* for the treated and untreated arms. These two means will then be compared using t-tests. For the primary analysis will use data from the saliva samples, and will then perform secondary analyses with data from the oral swab samples.

We will then address the hypothesis that subjects treated with chlorhexidine have lower abundance of *F. nucleatum* in the gastric cardia compared to those who did not receive treatment. We will calculate the mean absolute abundance of *F. nucleatum* in the cardia of the treated and untreated groups, and compare means using t-tests. We will then analyze data in a similar fashion from esophageal brushings in secondary analyses. All analyses will be 2- sided. For the primary analyses, statistical significance will be defined as  $p < 0.05$ .

We will perform numerous additional secondary analyses as part of this pilot study. For each subject and sample collected we will calculate the relative abundance of Gram-negative bacteria (%GNB). We will then make the same comparisons described above, with %GNB as the outcome. For these analyses we will use Wilcoxon rank sum tests instead of t-tests.

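### The stated 83% power overstates the planned two-sided t-test with 10 per arm (about 78%), and the enrolment target is given as both 20 and 22

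*Combined protocol and SAP*

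**What the plan says.** The Sample Size Considerations section states: "A sample size of 20 subjects (10 per arm) has 83% power" at alpha 0.05 for a difference of 1.3 SD in mean *F. nucleatum* between the groups. It gives no formula or software, and says that no published data were available to inform the calculation.

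The Statistics section fixes the test. For within-person change in saliva: "These two means will then be compared using t-tests". For the gastric cardia: "We will calculate the mean absolute abundance of *F. nucleatum* in the cardia of the treated and untreated groups, and compare means using t-tests". On sidedness: "All analyses will be 2- sided".

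On numbers, the sample size section continues: "We anticipate that 10% of enrolled subjects will be excluded, removed, or lost to follow-up", and then "We therefore plan to enroll 22 subjects". The design overview at the start of the protocol says instead: "We will enroll a total of 20 subjects".

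**The concern.** There are two problems, and both concern the same few sentences.

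First, sample size, allocation, effect size, alpha, sidedness and test are all given, so the power follows from the plan itself. It is not 83% for the test the plan names. At 10 per arm the SD is estimated with only 18 degrees of freedom. A formula that treats the SD as known ignores that cost.

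Second, the two enrolment statements use the same verb, so they cannot be read as one count of enrolled subjects and one of evaluable subjects. Losses are foreseeable: the Concomitant medications section removes from the final analyses anyone who takes antibiotics or immunosuppressive drugs during the study, including inhaled or nasal steroids.

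At stake is how a null result would be read. The sample size section itself allows for one and wants the data to inform later studies. A reader would take the chance of missing a true 1.3 SD effect to be 17% when it is 21.5%, or 26.5% if only 20 were enrolled and 10% were lost.

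**Working it through.** **Inputs.** From Sample Size Considerations: 10 per arm, standardised difference d = 1.3, alpha 0.05, stated power 83%, 10% loss, 22 enrolled. From Statistics: two-sided two-sample t-tests. From the design overview: 20 enrolled. The calculation assumes normal outcomes with a common SD.

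**Step 1: the plan's own figure.** The standardised shift is d × √(n₁n₂/(n₁+n₂)) = 1.3 × √(100/20) = 1.3 × √5 = 2.907. The two-sided normal approximation is

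Φ(2.907 − 1.960) = Φ(0.947) = 0.828.

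This rounds to 83%, so the stated figure is reproduced if the SD is treated as known.

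**Step 2: the planned test.** The two-sample t-test has 10 + 10 − 2 = 18 degrees of freedom, a two-sided critical value of 2.101 and noncentrality 2.907. The noncentral t distribution gives power 0.785. In 200,000 simulated trials, power was 0.786 for the pooled test and 0.781 for the Welch version. The shortfall is 83 − 78.5 = 4.5 points, and the type II error is 100 − 78.5 = 21.5%, against the implied 17%.

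**Step 3: what 10 per arm can detect.** Solving the t-test power for d gives 80% power at about 1.32 SD and 83% at about 1.38 SD.

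**Step 4: the two enrolment figures.** Expected retention is 22 × 0.9 = 19.8, about 20, and 20 × 0.9 = 18.

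| Evaluable subjects | Two-sided t-test power at 1.3 SD |
|---|---|
| 11 + 11 (22 enrolled, no loss) | 82.6% |
| 10 + 10 | 78.5% |
| 11 + 9 | 78.1% |
| 9 + 9 (20 enrolled, 10% loss) | 73.5% |

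Suppose instead that each subject is lost independently with probability 10%; this is an assumption, not in the plan. Expected power is then 77.6% to 77.8% with 22 enrolled and 73.1% to 73.3% with 20 enrolled. Each range depends on whether losses fall separately within each arm or leave the arms evenly split.

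**The case against.** The strongest reply is that 83% is not an arithmetic slip. It follows from the plan's inputs by a standard approximation, and since no formula is named, no stated calculation fails. That explains the number, but it does not make the sentence true of the planned test: the plan does not call the figure approximate, and it specifies a t-test with an SD estimated from 20 subjects.

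A second possible origin is the t-test with 11 per arm, which gives 82.6%. The source is therefore not certain. But the text attaches 83% to 10 per arm, and the expected 10% loss takes the trial from 22 subjects back to about 20.

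Rounding of the effect size does not rescue the figure either. At 1.35 SD, the top of what would round to 1.3, t-test power is 81.4%.

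On consequence, the objection has force. This is a pilot, the 1.3 SD has no empirical basis, 80% power needs only about 1.32 SD, and no stopping rule or go/no-go threshold depends on the figure.

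On enrolment, the sample size section does explain how 20 and 22 relate, and nothing suggests that the trial would follow the overview instead. The 73.5% is therefore what the overview's number would imply, not a forecast. The two sentences still disagree in the current text.

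**Conclusion.** The concern holds. For the two-sided t-test that the plan specifies, 10 per arm gives 78.5% power at 1.3 SD, not 83%, assuming normal outcomes with equal variance. The overstatement is 4.5 points and puts the only power figure in the plan above the conventional 80% when the planned test falls below it. The normal approximation is the likely but unconfirmed source.

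The enrolment statements of 20 and 22 conflict. Enrolling 22 with the anticipated loss keeps power near 78%; enrolling 20 would lower it to about 73% to 74%.

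Both points should be fixed. Neither undermines the design of a pilot of this size.

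**What to change.** In Sample Size Considerations, replace the power sentence with one saying that 10 evaluable subjects per arm give about 78% power to detect a 1.3 SD difference with a two-sided t-test at alpha 0.05 (80% for about 1.32 SD, 83% for about 1.38 SD). Name the method used.

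In the design overview, change the enrolment sentence to agree with the sample size section: 22 enrolled, about 20 evaluable. Strictly, 20/0.9 = 22.2, which rounds up to 23. Because 22 × 0.9 = 19.8, the difference is trivial and 22 can stand.

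The cost is two sentences and a slightly less favourable stated power. No test, endpoint or enrolment number in the sample size section needs to change.
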